# 6.5.4.2 Procedures for Premature Termination or Suspension of the Trial

In the event that the Sponsor, an IRB, or a regulatory authority elects to terminate or suspend the study or the participation of an investigational site, a study-specific procedure for early termination or suspension will be provided by the Sponsor; the procedure will be followed by applicable investigational sites during the course of termination or study suspension.

# 6.5.5 Criteria for Premature Termination or Suspension of an Investigational Site

# 6.5.5.1 Criteria for Premature Termination or Suspension of an Investigational Site

An investigational site may be terminated prematurely or suspended if the site (including the investigator) is found in significant violation of GCP, protocol, or contractual agreement, is unable to ensure adequate performance of the study, or as otherwise permitted by the contractual agreement.

# 6.5.5.2 Procedures for Premature Termination or Suspension of an Investigational Site

In the event that the Sponsor, an IRB, or a regulatory authority elects to terminate or suspend the study or the participation of an investigational site, a study-specific procedure for early termination or suspension will be provided by the Sponsor; the procedure will be followed by applicable investigational sites during the course of termination or study suspension.

#### 7.0 SELECTION AND DISCONTINUATION/WITHDRAWAL OF SUBJECTS

All entry criteria, including test results, need to be confirmed prior to the first dose of study drug.

#### 7.1 Inclusion Criteria

Subject eligibility is determined according to the following criteria prior to entry into the study:

- 1. In the opinion of the investigator or sub-investigator, the subject is capable of understanding and complying with protocol requirements.
- 2. The subject signs and dates a written, informed consent form prior to the initiation of any study procedures.
- 3. The subject is a Japanese healthy adult male, aged 20 to 60 years, inclusive, at the time of informed consent.
- 4. The subject weighs at least 50 kg and has a body mass index (BMI) from 18.5 to 25 kg/m^2, inclusive at Screening.
- 5. A male subject who is nonsterilized and sexually active with a female partner of childbearing potential agrees to use adequate contraception\* from the signing of informed consent to 12 weeks (84 days) after the last dose of study drug. The female partner of a male subject should also be advised to use adequate contraception\*.

\* Definitions and procedures for adequate contraception and pregnancy avoidance, and reporting responsibilities are defined in Appendix B.

[Justification for inclusion criteria]

Criteria 1, 2, 3 and 5 are set as standard criteria for the conduct of clinical pharmacological studies in healthy adults.

#### Criterion 4

Since whole blood collections of 400 mL from individuals weighing less than 50 kg is harmful to health according to the Act on Securing a Stable Supply of Safe Blood Products (Ministry of Health and Welfare [MHW] ordinance No. 22 in 1956) [11], the lower weight limit is set at 50 kg.

For BMI, Japanese subjects are to be within range of the standard weight according to the Criteria for Obesity Disease proposed by the Japan Society for the Study of Obesity [12].

#### 7.2 Exclusion Criteria

Any subject who meets any of the following criteria will not qualify for entry into the study:

- 1. The subject has received any investigational compound within 16 weeks (112 days) prior to the first dose of study drug.
- 2. The subject has received TAK-906 in a previous clinical study or as a therapeutic agent.

TAK-906	
Study ID TAK-906-1004	Page 26 of 71
Protocol	6 June 2017

- 3. The subject is an immediate family member of or an investigational site employee, or is in a dependent relationship with an investigational site employee who is involved in the conduct of this study (eg, spouse, parent, child, sibling) or may consent under duress.
- 4. The subject has uncontrolled, clinically significant neurologic, cardiovascular, pulmonary, hepatic, renal, metabolic, gastrointestinal, or endocrine disease or other abnormality, which may impact the ability of the subject to participate in the study or potentially confound its results.
- 5. The subject has a history of any psychiatric disease that would interfere with the evaluation of study drug activity (prolactin concentration) or safety.
- 6. The subject has a history of seizure or tardive dyskinesia.
- 7. The subject has a history of hyperprolactinemia, pituitary adenoma, and/or hypothyroidism.
- 8. The subject has a family history of prolonged QT.
- 9. The subject has undergone previous gastric bypass surgery or currently nad a gastric band fitted.
- 10. The subject has dysphagia and/or inability to swallow study medication whole.
- 11. The subject has a known hypersensitivity to any component of the TAK-906 formulation or related compounds.
- 12. The subject has a history of drug abuse (defined as any illicit drug use) or a history of alcohol abuse within 2 years prior to the Screening visit, or is unwilling to agree to abstain from alcohol and drugs throughout the study, or has a positive urine test result for drugs of abuse or a positive alcohol screen (urine alcohol test/breath test) result for alcohol at Screening.
- 13. The subject has taken any excluded medication, supplements, or dietary products during the time periods listed in the Excluded Medications, Supplements, and Dietary Products table in Section 7.3.
- 14. If male, the subject intends to donate sperm during the course of this study or for at least 12 weeks (84 days) after the last dose of study drug.
- 15. The subject has current or recent (within 24 weeks [168 days]) gastrointestinal disease that would be expected to influence the absorption of drugs (ie, a history of malabsorption, esophageal reflux, peptic ulcer disease, erosive esophagitis, frequent [more than once per week] occurrence of heartburn, or any surgical intervention).
- 16. The subject has a history of cancer, except basal cell carcinoma which has been in remission for at least 5 years prior to Day 1.
- 17. The subject has a positive test result for hepatitis B virus surface antigen (HBsAg), hepatitis C virus (HCV) antibody, human immunodeficiency virus (HIV) antibody/antigen, or serological reactions for syphilis at Screening.

TAK-906	
Study ID TAK-906-1004	Page 27 of 71
Protocol	6 June 2017

- 18. The subject has used nicotine-containing products (including but not limited to cigarettes, pipes, cigars, chewing tobacco, nicotine patch or nicotine gum) within 4 weeks (28 days) prior to the first dose of study drug. Cotinine test is positive at Screening.
- 19. The subject has poor peripheral venous access.
- 20. The subject has undergone whole blood collection of at least 200 mL within 4 weeks (28 days) or at least 400 mL within 12 weeks (84 days) prior to the start of study drug administration.
- 21. The subject has undergone whole blood collection of at least 800 mL in total within 52 weeks (364 days) prior to the start of study drug administration.
- 22. The subject has undergone blood component collection within 2 weeks (14 days) prior to the start of study drug administration.
- 23. The subject has a Screening or Check-in (Day -1) ECG that was abnormal (clinically significant).
- 24. The subject has a QTcF of >450 msec on the ECG at Screening, at Check-in (Day -1), or prior to the first dose of study drug (Day 1 predose).
- 25. The subject has abnormal Screening or Day -1 laboratory values that suggest a clinically significant underlying disease or any subject with the following lab abnormalities:
- Transaminase (ALT and/or AST) and/or total bilirubin >1.5 ×ULN.
- Creatinine >1.2 mg/dL.
- 26. The subject who, in the opinion of the investigator or sub-investigator, is unlikely to comply with the protocol or is unsuitable for any other reason.

#### [Justification for exclusion criteria]

Criterion 1 is set to specify a minimum interval not affected by any previous clinical trial in order to ensure the safety of subjects, in reference to "General Considerations for Clinical Trials" [13].

Criteria 2, 3, 4, 12, 13, 14, 16,17, 18, 19, and 26 are set as standard criteria for clinical pharmacological studies in healthy adults and in consideration of subjects' safety.

Criterion 5 is set due to the possibility of effects on safety and PD evaluations.

Criterion 6, 7, 8, 9, 11, 23, 24, and 25 are set in consideration of subjects' safety.

Criterion 10 is set due to the possibility of effects on PK evaluations.

Criterion 13 is set as a standard criterion for clinical pharmacological studies in healthy adults and in consideration of subjects' safety, and also due to the possibility of effects on PK evaluations.

Criterion 15 is set in consideration of subjects' safety and also due to the possibility of effects on PK evaluations.

TAK-906	
Study ID TAK-906-1004	Page 28 of 71
Protocol	6 June 2017

Criteria 20 to 22 are set in accordance with the Act on Securing a Stable Supply of Safe Blood Products (MHW ordinance No. 22 in 1956) [11].

#### 7.3 Excluded Medications, Supplements, Dietary Products

Use of excluded agents (prescription or nonprescription) or dietary products is outlined in Table 7.a.

28 days prior to treatment (Day 1)	7 days prior to treatment (Day 1)	7 days prior to treatment (Day 1)	24 hours prior to treatment (Day 1)
to Follow-up	to Follow-up	to Discharge (Day 8)	to Discharge (Day 8)

 
Prescription medications
 
	• Grapefruit/	
 
Vitamin supplements
 
	
 
Caffeine-containing
 

 
OTC medications
 
	grapefruit juice	
 
Alcohol-containing
 
	products

 
Neutraceuticals (St. John's wort, ginseng, kava kava, ginkgo biloba, and melatonin)
 
Chinese herbals
 
Immunization/Vaccines
 
Nicotine-containing products
 
	
 
Brassica vegetables (eg, kale, broccoli, watercress, collard greens, kohlrabi, Brussels sprouts, and mustard)
 
Charbroiled meats
 
	• Alconol-containing products	• Fruit juice

 Table 7.a
 Excluded Medications, Supplements, and Dietary Products

OTC=over-the-counter.

Note: If required to treat an AE, certain medications may be allowed after discussion and agreement between the Sponsor and the investigator.

Subjects must be instructed not to take any medications including over-the-counter (OTC) products, without first consulting with the investigator or sub-investigator.

# 7.4 Diet, Fluid, Activity

#### 7.4.1 Diet and Fluid

Subjects must abstain from all food and drink (except water) at least 8 hours before any clinical laboratory evaluations. On a day of study drug administration, subjects must not drink water, with the exception of water (240 mL) to take medication, between 1 hour prior to and 1 hour after dosing.

On the day of Check-in (Day -1), dinner will be consumed by 21:00. On Days 3 through 7, dinner will be taken at least 2 hours before evening doses (no evening dose on Day 7).

Breakfast must not be taken on the all days of study drug administration. The subjects must fast for 10 hours or more prior to and 4 hours after a single dose and all morning doses of trial medication in multiple dose periods.

An overview of the diet/meal considerations is presented in Table 7.b.

Cohorts 1, 2, and 3		
Day 1		
Approximate Time	Dose	Meal
08:00-09:00	X	No breakfast
12:00-13:00		Standard Lunch
19:00-20:00		Standard Dinner
Day 2		
Approximate Time	Dose	Meal
08:00-09:00		Standard Breakfast
12:00-13:00		Standard Lunch
19:00-20:00		Standard Dinner
Days 3 through 7		
Approximate Time	Dose	Meal
08:00-09:00	X	No breakfast
12:00-13:00		Standard Lunch
17:00-18:00		Standard Dinner (at least 2 hours before evening dose)
20:00-21:00	X (No evening dose on Day 7)	

Table 7.b	Overview of Diet/Meal Considerations
-----------	---

During hospitalization, subjects will take given meals and will not be allowed to take any other food. The caloric content and meal composition will be the same for each cohort.

After discharge, excessive eating or drinking should be avoided until all follow-ups are completed.

# 7.4.2 Activity

Supine positions are not allowed for 1 hour after dosing, unless irequired for examinations, etc.

Excessive exercise is not allowed during the study period. Subjects should do 15 minutes of light exercise a day during the hospitalization.

Blood donations are not allowed for at least 12 weeks (84 days) after the final examination in this study.

If a subject visits another medical institution during the study period, the investigator or sub-investigator should be informed of the visit in advance whenever possible, and should be reported the circumstances and therapy after visit. The investigator should communicate that medical institution about the subject's participation in the study.

No photosafety assessment has been performed to date with TAK-906; therefore, subjects should be cautioned to avoid exposure to direct sunlight during hospitalization.

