# 6.3 Rationale for Trial Design, Dose, and Endpoints

# 6.3.1 Rationale of Trial Design

In this study, a single dose period will be followed by a multiple dose period in each cohort

Therefore, combining single and multiple doses

in one study, with safety evaluations for at least 24 hours after the single dose is considered appropriate for the assessment of safety and PK in Japanese subjects receiving single and multiple doses of TAK-906 maleate. For each cohort, follow-up assessments will occur on Day 14 which is 7 days after completion of the last treatment dose, based on an 11 hour half-life ensuring that TAK-906 PK washout will be completed in 4 days.

Double-blind fashion using a matching placebo were selected for this first study in Japanese healthy male volunteers in order to adequately evaluate safety in Japanese subjects.

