There was little if any accumulation in serum prolactin concentrations with repeated dosing. As TAK-906 maleate dosing at 100 mg BID is predicted to be associated to nearly maximum prolactin production at steady state, 100 mg BID is considered an appropriate maximum dose for examination. This regimen was shown to be safe and well tolerated in non-Japanese subjects. In addition, this regimen was associated with a geometric means of AUC12 of 200.5 h\*ng/mL and  $C_{max}$  of 71.6 ng/mL as TAK-906 exposures in non-Japanese subjects, and provides approximately 15- and 27-fold margin in daily exposure compared with the exposures in female dogs, which are lower than those in male dogs (AUC 10800 and 5880 h\*ng/mL,  $C_{max}$  4340 and 1900 ng/mL in male and female dogs, respectively) observed at the dog NOAEL of 50 mg/kg/day, respectively. Modification of this dose level may be taken into consideration depending onpreceding Cohort 1 results, in which dose level will corresponding to the 50 mg BID starting dose.

In this study, a 10 mg BID dose regimen will also examined in Cohort 3. The regimen was selected to enable safety, PK, and PD evaluations over a wider dose range than that for the multiple dose period in the foreign phase 1 study. This cohort will be conducted in parallel with the other cohorts of 50 mg BID or 100 mg BID.

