## 9.3.4 Confinement

In either Cohort 1, 2, or 3, each subject will be confined from Day -1 to the morning of Day 8 and discharged after the investigator's or sub-investigator's confirmation of no significant abnormality in his health through physical examination and tests on Day 8, at 24-hour post morning dose of Day 7.

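### The sunlight caution in Protocol 7.4.2 ends at discharge, 24 hours after the last dose, although the reason given for it concerns the drug and not the confinement

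*Protocol*

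**What the plan says.** Protocol 7.4.2 (Activity) gives the reason and the end point together: photosafety has not been assessed, so "subjects should be cautioned to avoid exposure to direct sunlight during hospitalization". Protocol 9.3.4 fixes what hospitalization means: "each subject will be confined from Day -1 to the morning of Day 8", with release 24 hours after the Day 7 morning dose. There is no Day 7 evening dose, so release is also 24 hours after the last dose.

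Protocol 6.3.1 places the follow-up visit on Day 14, 7 days after the last dose, "based on an 11 hour half-life ensuring that TAK-906 PK washout will be completed in 4 days".

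Other restrictions have mixed end points:

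- **Ending at discharge:** vitamin supplements, alcohol, caffeine and fruit juice (two columns of Table 7.a in Protocol 7.3).
- **Running past discharge:** the other two columns of Table 7.a, which go to Follow-up (among them medicines and grapefruit); meals in 7.4.1 ("After discharge, excessive eating or drinking should be avoided until all follow-ups are completed"); and, in 7.4.2 itself, exercise ("Excessive exercise is not allowed during the study period") and blood donation ("Blood donations are not allowed for at least 12 weeks (84 days) after the final examination in this study").

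Nothing in the supplied protocol or SAP carries the sunlight caution beyond discharge.

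**The concern.** The precaution rests on a property of the compound that nobody has tested. Discharge changes where the subject is but does not change that property. If drug is still present, the stated reason still applies, and the written caution stops just as subjects become outpatients and the site can no longer limit their time outdoors.

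An end point tied to the ward also treats early leavers unevenly. Protocol 7.7 lets a subject withdraw at any time. If he then leaves less than 24 hours after a dose, the caution ends sooner still. The documents do not say when such subjects are released.

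What is at stake is a subject-safety instruction for healthy volunteers. No endpoint, analysis or stopping rule depends on it.

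**Working it through.** **Inputs**

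- Half-life 11 h and washout 4 days = 96 h (Protocol 6.3.1).
- Discharge 24 h after the last dose (Protocol 9.3.4).
- 100 mg BID: AUC12 200.5 h*ng/mL and Cmax "of 71.6 ng/mL as TAK-906 exposures in non-Japanese subjects" (Protocol 6.3.2).
- 50 mg BID at steady state: AUC24 116 h*ng/mL, Cmax 31.2 ng/mL (Protocol 6.3.2). I assume equal intervals, so 116/2 = 58 per 12 h.
- For 10 mg BID no exposure is given, and for metabolite M23 no half-life.

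**The protocol's own figure.** 96/11 = 8.73 half-lives; 0.5^8.73 = 0.24% remaining. A 4-day washout agrees with an 11-hour half-life.

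**Uncovered time**

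- Half-lives elapsed at discharge: 24/11 = 2.18.
- To five half-lives (assumed rule): 5 × 11 − 24 = 31 h.
- To the 4-day washout: 96 − 24 = 72 h, that is, Day 8 to Day 11.

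**Ceiling on the plasma level at discharge.** Put the whole steady-state AUC into the 11-hour phase.

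- k = ln 2/11 = 0.0630 per h.
- The integral of exp(−kt) over 0–12 h is 8.42 h, and exp(−24k) = 0.220.
- 100 mg BID: 200.5/8.42 = 23.8; × 0.220 = 5.2 ng/mL; 5.2/71.6 = 7.3% of Cmax.
- 50 mg BID: 58/8.42 = 6.9; × 0.220 = 1.5 ng/mL; 1.5/31.2 = 4.9% of Cmax.

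This is generous. It implies a starting level of 23.8 ng/mL at 100 mg BID, against a stated Cmax of 71.6.

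**Using Cmax and AUC together.** Take a peak equal to Cmax at time 0, then a fast phase with an assumed half-life, then the 11-hour phase. With F the integral of the fast exponential over 0–12 h, the starting level of the slow phase is B = (AUC − Cmax × F)/(8.42 − F), and the level at 24 h is 0.220 × B. For example, at 100 mg BID with a 1 h fast half-life, F = 1.44, B = (200.5 − 71.6 × 1.44)/(8.42 − 1.44) = 13.9, and the level is 3.1 ng/mL.

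| Assumed fast half-life | 100 mg BID, ng/mL at 24 h | 50 mg BID, ng/mL at 24 h |
|---|---|---|
| 0.25 h | 4.8 (6.7% of Cmax) | 1.3 (4.1%) |
| 0.5 h | 4.3 (6.0%) | 1.0 (3.3%) |
| 1 h | 3.1 (4.3%) | 0.41 (1.3%) |
| 1.25 h | not computed | 0.06 (0.2%) |
| 1.5 h | 1.6 (2.3%) | none: slow phase is zero from 1.29 h |

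At 100 mg BID the slow phase reaches zero at a fast half-life of 1.97 h. The documents do not fix the fast half-life, so the level at discharge is a range: near zero to about 5 ng/mL, and near zero to about 1.5 ng/mL.

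**By 96 h**, the same ceiling gives 23.8 × 0.0024 = about 0.06 ng/mL at 100 mg BID.

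**Who this covers.** At most 2 × 6 = 12 active subjects, because the Cohort 2 dose may be lowered (Protocol 6.4). The 6 active subjects on 10 mg BID have no exposure figure to work from.

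**The case against.** The strongest reply is that discharge is a legitimate choice. The caution is precautionary: it answers an absence of data, not a signal. It covers every dosing day, when exposure is highest, and 24 hours more. Table 7.a uses the same end point for four items. The documents do not say that the restrictions running past discharge do so because of residual drug, so they show only that discharge is not a uniform rule. All of this stands, and it is why the point is an improvement and not an error.

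Two stronger readings are tempting, and the documents do not support them.

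- **That 7.4.2 contradicts the protocol's own washout.** Section 6.3.1 uses the 4 days to justify the Day 14 visit and sets no photosafety criterion. The 72 hours depend on borrowing that figure; five half-lives gives 31.
- **That a large amount of drug remains at discharge.** Single-phase decline at 11 hours leaves 22% after 24 hours (0.5^2.18), but that is not 22% of Cmax. Likewise, taking the 12-hour level as the interval mean gives 200.5/12 × 0.469 = 7.8 ng/mL at 100 mg BID. That needs an essentially flat profile, which a Cmax of 71.6 with an AUC12 of 200.5 rules out (200.5/71.6 = 2.8 h). About 5 ng/mL is the ceiling.

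The unseen material also matters. Protocol 13.2 says the consent form sets out what is required of participants, and Protocol 4.3 refers readers to the Investigator's Brochure. Either may already give sunlight advice after discharge. The point therefore concerns only the end point written in 7.4.2.

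**Conclusion.** The point holds as a cheap improvement of low weight. The written caution stops 24 hours after the last dose, while its stated reason lasts as long as drug is present. The uncovered time is 31 hours under an assumed five-half-life rule, or 72 hours to the end of the 4-day washout. Residual TAK-906 at discharge is at most about 5 ng/mL (7% of Cmax) at 100 mg BID and about 1.5 ng/mL (5%) at 50 mg BID, and may be near zero.

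These levels assume that non-Japanese exposures apply, that the late decline has an 11-hour half-life, and that the 50 mg AUC24 splits evenly. The two time gaps need no concentration model.

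The expected gain is small. The documents report no phototoxicity signal. A skin reaction would still be recorded, since adverse events are collected to Day 14 (Protocol 10.2.9.1) and the Day 8 and Day 14 physical examinations include the skin (Protocol 3.0 and 9.2.1). Recording a reaction does not prevent it, however, and these subjects have nothing to gain from the drug itself.

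**What to change.** In Protocol 7.4.2, replace 'during hospitalization' with 'from the first dose until 4 days after the last dose', which is Day 11 for a subject who completes dosing. Repeat the caution at discharge, including for anyone who leaves confinement early; counting from the last dose covers that case. If the consent form or Investigator's Brochure already gives this advice, a cross-reference in 7.4.2 is enough.

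The cost is one phrase in the protocol and one line in the discharge instructions. Completers accept a minor restriction for about 3 more days. No visit, procedure or data item is added.

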#### 7.5 **Documentation of Subjects Failure**

The investigator or sub-investigator must account for all subjects who sign informed consent. If a subject is withdrawn from the study before the first study drug administration, the investigator or sub-investigator should complete the electronic case report form (eCRF).

Primary reasons for subject failure are to be recorded in the eCRF using the following categories:

- Death.
- AE.
- Screen Failure (failed inclusion criteria or did meet exclusion criteria) <specify reason>.
- Protocol deviation.
- Lost to follow-up.
- Withdrawal by subject <specify reason>.
- Study terminated by Sponsor.
- Sample size sufficient.
- Other < specify reason>.

Subject identification numbers assigned to subjects who fail screening should not be reused. However if a reserve subject is to participate in another cohort, the same subject identification number may be used.

